#### Exploratory Objective: Psychological Health

- We will use the ASEBA-web Youth-Self Report (YSR) scores that align with the DSM-V. We will compare depressive problems scores, anxiety scores and attention scores from the two groups.

#### Missing Data

We will use descriptive statistics (n for each measure) to quantify and report the extent of any missing data. Reasons for missing data will be clearly documented, categorized, and reported in publications. We will use the multiple imputation technique, which involves generation of multiple data sets with imputed values, which are then pooled. From this pooled imputed data set, we will conduct sensitivity analyses to assess the effect of the imputations on the results and compare the findings with and without the imputations to verify the strength of our results.

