Maternal Choline Supplementation and Offspring Cognition in Adolescence

NCT05859126

28 June 2024

This study seeks to test the general hypothesis that maternal choline intake of 930 mg/d throughout the 3rd trimester of pregnancy, compared to 480 mg/d, causes offspring to have superior cognitive functioning. Three domains of cognition will be examined to test three independent hypotheses about the effects of the intervention on (1) sustained attention, (2) executive functioning, and (3) memory.

Sample Size:

The sample size was determined by the original controlled feeding study, which was designed to detect group differences for that study's primary endpoints—biomarkers of choline status—for which it was estimated that a sample size of 26 (13 per treatment group) would achieve 80% power to detect a moderate effect size at an  $\alpha$  of 0.05. The sample sizes for the ancillary longitudinal follow-up studies to investigate treatment effects on infant and child cognitive outcomes was limited by the original sample size, minus loss to follow-up. The results of these studies demonstrated that (1) a sample size of 24 (12 per group) was sufficient to detect a statistically significant treatment effect of the prenatal choline intervention on infant processing speed (Caudill, et al., 2018) and (2) that a sample size of 20 (11/9 participants from the 930/480 mg choline/d groups, respectively) was sufficient to demonstrate group differences on several cognitive outcomes age 7 years. No further sample size calculations were conducted for this 14-year follow-up study because the sample was limited to those included in the original feeding study, which was sufficient to see the effect of choline on cognition. We hypothesize that the cognitive effects of the prenatal supplementation should endure into adolescence, and we expect that the cognitive outcomes will be measured with much greater precision at age 14 years than during infancy or at 7 years, thus we expect to have adequate power to detect similarly moderate to large effect sizes.

Descriptive Statistics:

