Univariate and bivariate descriptive statistics and graphs will be examined to assess data value plausibility. Descriptive statistics for sample characteristics, by group, will be presented in tables. Continuous variables will be summarized with means and standard deviations, and categorical variables will be summarized with absolute counts and relative frequencies. A table of sample characteristics will include participant sex, level of education, parental level of education, native language, family income, history of head injury absence/presence, and concurrent medications and supplements. We will also provide a flow chart detailing participant attrition and missing data.

Inferential Statistical Analysis:

Acknowledging the risks inherent with utilizing multiple endpoints in a small sample, we generated an *a priori* analysis plan, with specific objectives in alignment with the areas of cognition of interest. For each cognitive objective, we have detailed the tasks and outcome variables that will be used for its measurement.

Objective 1 Sustained Attention: Estimating the effect of maternal third trimester choline intake on offspring **sustained attention** at age 14 years.

- **Sustained Attention** will be measured using the Rapid Visual Information Processing task (RVP) of the Cambridge Neuropsychological Test Automated Battery (CANTAB).
  - **The primary outcome for this objective will be the nonparametric index of detection sensitivity, A-prime.**
    - A-prime will be analyzed using a general linear model with fixed effects of treatment group and participant sex.

Objective 2 Executive Functioning: Estimating the effect of maternal third trimester choline intake on offspring **executive functioning** at age 14 years.

- Our primary outcome for this objective will be a composite measure of executive functioning (EF) derived from key variables obtained from multiple tasks that assess four core components of EF: planning, working memory, inhibitory control, and attentional flexibility. All tasks are administered using the CANTAB platform.
  - **Planning** will be assessed by two versions of a Towers of London task. The key outcome variable from the **Stockings of Cambridge task (SOC)** will be the **number of perfect solutions across all problems**. From the **One Touch Stockings of Cambridge task (OTS)** the **key outcome** variable will be the number of problems solved on the first attempt.

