  - **Working Memory** will be assessed using the **Spatial Working Memory task (SWM)** and the Backward Digit Span task (BDS). The key outcome variable for SWM will be the total number of search errors and span length for BDS.
  - **Inhibitory control** will be assessed using the **Cambridge Gambling Task (CGT)**. The key outcome variable will be the delay aversion total score.
  - **Attentional flexibility** will be assessed using the **Intradimensional-Extradimensional Shift task (IED)**. The key outcome variables will be the total number of choice errors.
- The EF composite (EFcomp) outcome variable will be defined as the average z-score of the individual key EF task outcomes as follows: EFcomp = (zSOC perfect solutions+ zOTS first attempt correct+ zSWM search errors+ zBDS span length+ zCGT delay aversion+ zIED choice errors) / 6

with the z-score calculated by the sample mean and standard deviation:

$$z = \frac{\text{raw score} - \bar{x}_{\square}}{sd_{\square}}$$

Statistical analysis of EFcomp will be conducted using a general linear model with fixed effects of treatment group and participant sex.

Objective 3 Memory: Estimate the effect of maternal third trimester choline intake on offspring **memory function** at age 14 years.

- Our primary outcome for this objective will be a composite measure of memory function derived from multiple tasks assessing episodic memory, recognition memory, and working memory. All tasks are administered using the CANTAB platform.
- **Episodic memory** will be assessed by a Verbal Paired Associate Learning task (VPA) and a nonverbal **Paired Associate Learning task (PAL)**. The key outcome for both tasks will be the total number of errors.
- **Recognition memory** will be assessed by the **Delayed Match to Sample task (DMS)** and the **Pattern Recognition Memory task (PRM)**. The key outcome for both tasks will be the proportion of correct choices on delay trials.
- **Working memory** will be assessed using two span tasks: **nonverbal spatial span (SSP)** and verbal forward digit span (FDS). The key outcome variable for both will be span length.

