- The memory composite ( $MEM_{comp}$ ) outcome variable will be defined as the average z-score of the individual key outcomes from the memory tasks as follows:  $MEM_{comp} = (zVPA \text{ total errors} + zPAL \text{ total errors} + zDMS \text{ proportion correct} + zPRM \text{ proportion correct} + zSSP \text{ span length} + zFDS \text{ span length}) / 6$

with the z-score calculated by the sample mean and standard deviation:

$$z = \frac{\text{raw score} - \bar{x}_{\square}}{sd_{\square}}$$

Statistical analysis of  $MEM_{comp}$  will be conducted using a general linear model with fixed effects of treatment group and participant sex.

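### As worded, the SAP analyses one pooled imputed data set, which leaves out between-imputation variance and makes the imputed standard errors too small; the effect is near nil when only one composite task is missing

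*SAP*

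**What the plan says.** The Missing Data section of the SAP chooses multiple imputation and describes it as "generation of multiple data sets with imputed values, which are then pooled". The next sentence begins the analysis from the product of that step: "From this pooled imputed data set, we will conduct sensitivity analyses to assess the effect of the imputations on the results". The stated purpose is to "compare the findings with and without the imputations to verify the strength of our results".

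The analyses to be repeated are set under the three objectives. For Objective 1, "A-prime will be analyzed using a general linear model with fixed effects of treatment group and participant sex". Objectives 2 and 3 use the same model on composites. The executive-function "outcome variable will be defined as the average z-score of the individual key EF task outcomes as follows", and both composites are standardised within the study, "with the z-score calculated by the sample mean and standard deviation".

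The SAP does not give the number of imputations, the imputation model, the expected amount of missing data or the number of participants at age 14.

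**The concern.** Multiple imputation gives honest standard errors because the model is fitted in each completed data set and the spread of the estimates between sets is added to the variance. In the SAP the data sets are what is pooled, and a single data set is what is analysed. One fit to one data set contains no between-imputation term, so imputed values are treated as if they had been observed.

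The composites raise a related question of order. The mean and SD used for the z-scores differ between imputed sets, and the SAP does not say whether standardising comes before or after pooling.

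What is at stake is the robustness check. If the imputed analysis has standard errors that are too small, its agreement with a positive non-imputed result is weaker evidence than it appears, and it can also turn a null result significant. In a sample of about 20, one or two absent scores are already 5-10% of the data.

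**Working it through.** The SAP gives no figure on this point to reproduce, so the check is a derivation followed by simulation.

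**Inputs.** From the SAP: linear model on group and sex (3 parameters); 20 participants split 11/9, the age-7 sample in the Sample Size section. Assumed: the same split at age 14, sex random, scores missing completely at random, proper Bayesian regression imputation, m = 20, no true effect, two-sided 5%. 'Averaged' means the model is fitted once to the mean of the imputed data sets.

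**Correct combination.** With estimates Q_j and variances U_j from the m sets, the total variance is T = mean(U_j) + (1 + 1/m)B, where B is the variance of the Q_j. The averaged data set has no B term.

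**Hand check for A-prime, imputed from group and sex.** With many imputations the averaged values of k missing participants fall on the line fitted to the other n - k. The estimate is then unchanged, but two things shrink. The residual variance is divided by n - 3 instead of n - k - 3, and the design counts n participants instead of n - k. So SE(averaged)/SE(non-imputed) is about the square root of [(n - k - 3)/(n - 3)] x [(n - k)/n]:

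- k = 1: sqrt(16/17 x 19/20) = 0.946
- k = 2: sqrt(15/17 x 18/20) = 0.891
- k = 4: sqrt(13/17 x 16/20) = 0.782

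The critical value on 17 df is 2.110. Multiplied by these ratios it becomes 1.995, 1.880 and 1.650. The two-sided tails of t on 16, 15 and 13 df beyond those points are 6.3%, 8.0% and 12.3%.

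**Simulation for A-prime, 20,000 runs** (Monte Carlo SE 0.15-0.24 points), imputed from group and sex:

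| Missing of 20 | Non-imputed | Averaged | Rubin, Barnard-Rubin df |
|---|---|---|---|
| 1 | 5.1% | 6.6% | 4.8% |
| 2 | 4.9% | 8.2% | 4.4% |
| 4 | 5.1% | 12.8% | 4.4% |

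In a separate set of 4,000 runs with 1, 2 and 4 missing, the mean averaged SE was 0.441, 0.428 and 0.401, while the estimate's actual SD was 0.480, 0.490 and 0.525. The mean Rubin SE was 0.472, 0.491 and 0.537. With m = 5 the averaged error was much the same (8.1% and 12.4% with 2 and 4 missing).

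**Sensitivity to the imputation model.** Adding two task scores correlated 0.5, or four correlated 0.3, gave averaged type I error of 5.8-6.2%, 6.6-7.5% and 9.5-10.8% with 1, 2 and 4 missing.

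**Composites** (signs as in the SAP formulas, higher delay aversion taken as worse, |r| = 0.3, z-scores recomputed in each set), type I error with 1/2/4 participants affected:

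| Missing | EF averaged | EF Rubin | Memory averaged | Memory Rubin |
|---|---|---|---|---|
| One task | 5.0/5.6/6.0% | 4.5/4.5/4.0% | 4.9/5.5/5.9% | 4.4/4.6/4.2% |
| All six tasks | 6.1/8.7/11.9% | 4.0/4.2/2.4% | 6.5/8.1/12.5% | 4.3/3.6/2.7% |

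**Effect on the robustness comparison (A-prime).**

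- When the non-imputed test had falsely rejected, the averaged analysis agreed in 100% of runs with imputation from group and sex, and in about 90-95% with correlated scores added. With imputation from group and sex, Rubin's rules agreed in 91%, 87% and 80% with 1, 2 and 4 missing. These conditional rates are less stable: repeat runs gave 84% with two missing and 73-79% with four.
- When the non-imputed test had not rejected, averaging from group and sex added a false rejection in 288/18,977 = 1.5%, 648/19,018 = 3.4% and 1,550/18,983 = 8.2% of runs, against 0.1-0.3% with Rubin's rules.
- With a true effect of 1 SD and imputation from group and sex, Rubin's rules failed to confirm about 5-12% of correct rejections, rising with the number missing.

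**The case against.** The best defence is that pooling is the usual name for the combining step of multiple imputation. A trained analyst would probably pool estimates whatever the sentence says. That is possible. But two consecutive sentences make the data sets the thing pooled and then analyse one data set, and no other section corrects this. The wording is wrong as it stands, not merely short of detail.

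A second defence is that every figure rests on assumptions, including averaging, which the SAP does not mention. That stands for the size, but not for the direction: the standard error was too small at every missing rate tried, with or without correlated scores in the imputation model.

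Third, Rubin's rules are not a perfect referee. Under missingness completely at random there is no bias to detect, so some of their disagreement is imputation noise and wider intervals, and they miss some true effects. That stands too.

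Three stronger readings are tempting and are not supported:

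- *The check cannot fail.* The 100% agreement belongs to imputation from group and sex alone, a model the SAP does not name.
- *Type I error is near 70%.* That follows from stacking 20 copies and counting each participant 20 times; the SAP does not say the sets are stacked.
- *The main results are compromised.* The imputed analysis is described only as a sensitivity analysis.

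**Conclusion.** The point holds as a fault in the wording of a sensitivity analysis, and it should be fixed. Under the stated assumptions the inflation is modest with one A-prime score missing and material with four: 6.6% to 12.8%, or about 6% to 10% with a richer imputation model. It is similar when whole composites are missing, and practically absent when a single component task is missing. The robustness comparison is therefore tilted towards confirming a positive result, without being guaranteed to do so. The non-imputed linear model is untouched, and with complete data the issue disappears. The SAP gives no indication of how much will be missing, so the actual size in this trial cannot be stated.

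**What to change.** Replace the last two sentences of the Missing Data section with:

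> Missing scores will be multiply imputed, with the number of imputations fixed in advance. In each imputed data set the z-scores and composites will be computed and the general linear model on treatment group and sex fitted; treatment estimates and variances will be combined by Rubin's rules with small-sample (Barnard-Rubin) degrees of freedom and compared with the non-imputed results.

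If pooled estimates were meant all along, this simply says so, and it also settles when the z-scores are computed. The text covers the three primary outcomes. The exploratory psychological scores, for which the SAP states no model, would need their comparison run in each set in the same way if they are imputed. Naming the variables in the imputation model would be useful, since the results above depend on them, but the repair does not require it.

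The cost is wording only. Intervals in the imputed analysis widen: for A-prime imputed from group and sex, the averaged SE is about 0.94, 0.87 and 0.75 of the Rubin SE with 1, 2 and 4 missing. Rubin's rules are somewhat conservative when whole composites are imputed (2.4-2.7% with 4 of 20 missing). If A-prime is imputed from group and sex alone, the imputed analysis will add little to the non-imputed one.

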#### Secondary, post-hoc, and exploratory analyses

Given our small sample size, the complexity of the interpretation of cognitive tests, and the novelty of this research. We will, as appropriate conduct additional planned secondary and

sensitivity analyses, in addition to post-hoc exploratory analyses to better understand our data to arrive at the fullest possible understanding of the effects of the intervention.
